As highlighted above, we aim to undertake a QED with PSM to ascertain impact. The PSM study will consist of collecting data from the treatment group (from the four RT hospitals) and then, with the support of the relevant health informatics teams at the sites, identify a suitable group of controls who have not used the service from at least one of the existing sites (but who have not refused that service as including those who refuse service would create a selection bias). This could be drawn from contemporaneous or historical data, depending on the processes RT uses to gather referrals; for example, whether there would be a group of suitable CYP not approached by RT. This data will be provided to us without any personal identifying information. The groups will then be propensity score matched to identify the most suitably similar controls based on a variety of demographic and clinical data that we have in both the hospital record and RT dataset. This is likely to include age, gender, severity and nature of their injury, or level of risk to the CYP based on RT's eligibility criteria (weapon-related injury or a serious assault with the intention to do serious harm; concerns that incidents or individuals may be gang affiliated or have been exposed to or experienced violence/abuse; concerns that an individual is at risk of further harm or abuse; concerns or disclosures of domestic abuse, sexual violence, including historic sexual violence/abuse; concerns of (Child) Sexual Exploitation or (Child) criminal exploitation). These variables are chosen because they are related to both the treatment and the outcome and are common in the literature (see e.g. Shibru et al., 2007).

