The matching is done by comparing the probability that an individual is assigned to the treatment group. Therefore, a matched pair comprises two individuals with the same probability of being assigned to the treatment group, yet one of them belongs to the control group. This probability is called the propensity score. The first step of PSM is to use logistic regression to calculate the propensity scores of each individual in the sample; the second step is to match these individuals according to their propensity scores. Once a propensity score has been calculated for each observation, we will ensure that there is overlap in the range of propensity scores across treatment and comparison groups by examining the scores graphically. A second check for the quality of matching is that, the propensity scores should have a similar distribution ("be balanced") in the treated and comparison groups. We will obtain an estimate of the propensity score's distribution by splitting the sample by quintiles of the propensity score. Because the number of individuals in the control group might be different than those in the treatment group, we will use kernel-based matching. We prefer the Epanechnikov kernel with a bandwidth of 0.06, which are common choices in the literature (see, e.g., Heckman, Ichimura and Todd, 1997).

We will ensure that there is a data sharing agreement between UoB and RT and UoB and the participating NHS trusts to support these activities.

Outcomes

For contextual information, following a co-design stage working with the intervention providers, it became clear that the primary outcome should be readmission (specifically violence/abuse related) to hospital at 12 months. These data are available for both intervention and controls and we are confident that there will be sufficient power to distinguish the two groups as well providing a comparable estimate with the published literature. The key secondary outcomes will be mortality by any cause one-year post contact with RT (this will draw on NHS data captured in the Summary Hospital level Mortality Indicator and other data which captures mortality beyond 30 days post discharge). We also plan to pilot the collection of the strengths and difficulty questionnaire (SDQ) and self-report delinquency scale (SRDS). However, the latter will be piloted in the opening phases of the study, as it is not likely we will be able to collect this data on control groups.

Control quantitative data

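### Matching quality is judged on the propensity score itself, and that check can pass while measured covariates, especially age spread and joint distributions, stay imbalanced

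*Protocol*

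**What the plan says.** The matching method is set out in the protocol under Impact evaluation activities, Control group data collection. The covariates are provisional: "This is likely to include age, gender, severity and nature of their injury, or level of risk to the CYP", the last based on Redthread's eligibility reasons. The score model is given in one sentence: "The first step of PSM is to use logistic regression to calculate the propensity scores of each individual in the sample". Nothing is said about curved or interaction terms. Matching is by kernel: "We prefer the Epanechnikov kernel with a bandwidth of 0.06".

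Two checks follow. On overlap: "we will ensure that there is overlap in the range of propensity scores across treatment and comparison groups by examining the scores graphically". On balance, it asks that "the propensity scores should have a similar distribution" in the treated and comparison groups, and gives the method: "We will obtain an estimate of the propensity score's distribution by splitting the sample by quintiles of the propensity score".

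The Impact data analysis section then fixes the order of work. A descriptive comparison of the groups comes first and matching second. The average difference and its t-test come next. Matching is described as the step that removes the systematic differences. Rosenbaum bounds are added for covariates that were not observed.

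**The concern.** The purpose of matching on a score is to make the groups alike on the covariates. Balance on an estimated score implies balance on the covariates only if the score model is adequate, and a check made on that same score does not test this.

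No other stated step fills the gap. The one covariate comparison precedes matching, so it does not describe the weighted sample from which the effect is estimated. The Rosenbaum bounds address unobserved confounders, not poor balance on observed ones. As written, the plan could accept a match that leaves measured confounders unequal and go straight to the test.

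The design makes this more than a formality. Children enter the programme through clinician referral or Redthread's own review of hospital records, and controls may be historical. Selection that depends on age and referral reason in combination is plausible.

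**Working it through.** **Inputs from the protocol.** Logistic score, functional form unstated; Epanechnikov kernel, bandwidth 0.06; ages 10 to 17; 392 per group for d = 0.2 at 80% power; illustrative control risk 7.8%; about 150 engaged in the pilot.

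**The plan's own figure.** n = 2(z₀.₉₇₅ + z₀.₈)²/d² = 2 × 2.8016²/0.04 = 392.4 per group. Two-sided 5% is assumed because the protocol states no alpha. The 392 is reproduced. It serves here only to size the illustration.

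**Why the score balances regardless.** A control with score pⱼ gets weight proportional to 0.75(1 − u²), with u = (pᵢ − pⱼ)/0.06, and zero once |u| ≥ 1. For every matched treated child, the weighted mean control score is therefore within 0.06 of that child's own score. This holds for any score, right or wrong.

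**An extreme case by hand.** Take equal groups, with treated ages 10, 11, 16, 17 and control ages 12, 13, 14, 15. Both means are 13.5. A logistic model linear in age has fitted slope zero, because Σ(tᵢ − ½)ageᵢ = ½(54 − 54) = 0. Every score is 0.5, so overlap and score balance are perfect, yet no age is shared. The standardised mean difference (SMD) for age is also zero. Only the spread shows the problem: the variances are (12.25 + 6.25)/2 = 9.25 and (2.25 + 0.25)/2 = 1.25, a ratio of 7.4.

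**Simulation.** All coefficients are assumed. There were 300 datasets per setting, no treatment effect, a main-effects logistic score on age, sex, weapon injury and severity (0 to 3), and the protocol's kernel. Let a = (age − 13.5)/2.3.
- Selection not captured by the fitted model: logit = −0.2 + 0.2a + 0.2 male + 0.9(a² − 1) + 1.2(weapon − 0.3)(severity − 1.5).
- Selection captured: logit = −0.2 + 0.2a + 0.3 male + 0.6 weapon + 0.3(severity − 1.5).
- Outcome in both: logit = −2.9 + 0.7(a² − 1) + 0.9(weapon − 0.3)(severity − 1.5) + 0.2 male.

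| After matching | Not captured, 392 | Not captured, 150 | Captured, 392 | Captured, 150 |
|---|---|---|---|---|
| Mean score SMD | 0.048 | 0.042 | 0.023 | 0.023 |
| Largest quintile-share gap (points) | 7.5 | 7.3 | 2.3 | 3.4 |
| Mean SMD, age squared | 0.68 | 0.67 | 0.01 | 0.01 |
| Mean SMD, weapon × severity | 0.43 | 0.42 | 0.02 | 0.03 |
| Spurious risk difference (points) | 4.2 | 4.2 | 0.2 | 0.2 |
| Score SMD below 0.1 | 99.7% | 99.7% | 100% | 100% |
| … and a listed covariate's mean SMD above 0.1 | 1.7% | 9% | 0% | 4.7% |
| … and age squared or weapon × severity above 0.1 | 99.7% | 99.7% | 27% | 61% |

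The protocol sets no pass mark, so a score SMD below 0.1 is my stand-in for passing.

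**Other assumed coefficients.** Omitting age-squared and age-by-weapon terms at three rising strengths gave residual bias of 0.7, 1.1 and 1.8 points (0.3 with none omitted). A further set gave 2.0 points (0.1 with a correct model). The mean score SMD was 0.015 to 0.032 in these settings.

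**Scale.** From a 7.8% control risk, an arcsine effect of 0.2 gives sin²(arcsin√0.078 − 0.1) = 3.3%, a difference of 4.5 points. The linear version, 0.2 × √(0.078 × 0.922), gives 5.4 points. These are individual-level conversions, the basis of the 392, and not the protocol's illustration of 30 against 31 readmissions. A spurious 4.2 points is nearly as large as the target effect; 0.7 points is about a sixth of it.

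**The case against.** **The protocol does not rule out other diagnostics.** It describes a second check, not the last one. The covariate list is provisional, and balance tables and thresholds are often left to an analysis plan, which is not at hand. A reader might infer that covariate balance will never be examined; the text does not say that. What stands is narrower: the protocol does choose a measure of matching quality, and it aims that measure at the score.

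**The pilot draws no causal conclusions.** The Sample size section says so, and an efficacy study would have its own protocol. This lowers the immediate stakes. It does not remove them, because the Success criteria section allows pilot data to enter the final analyses, and the pilot exists to try out the methods.

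**A main-effects score tends to balance covariate means.** This is largely right. A reader might infer that a listed covariate will usually be visibly off. One set of assumed coefficients gave an SMD above 0.1 for some listed covariate in 94% of runs at 392 per group; the setting tabulated above gave 1.7%. Even with every true term in the model, 0 to 47% of runs exceeded 0.1 at 392 per group, depending on the strength of selection. No single rate can be attributed to misspecification.

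**The quintile check is not powerless.** The gap in quintile shares was 7.5 points when selection was not captured and 2.3 when it was. An attentive analyst might notice, but the protocol gives no size at which to act.

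**Conclusion.** The point holds in a limited form. Overlap and score balance are legitimate checks, but neither shows that the matched groups are alike on the measured covariates. The score check can pass while age spread and joint distributions, such as age or severity by injury or risk type, remain imbalanced and bias the estimate. That much rests on the wording and on how kernel weights work, and the hand example shows it without any assumed coefficient.

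The size is not established. Residual bias ran from 0.7 to 4.2 points across the assumed settings with omitted terms, and from 0.1 to 0.3 points where the score model was adequate. A reader might infer that the effect estimate will be biased. The documents do not support that, because neither the true selection process nor the final form of the score model is known.

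**What to change.** Keep the overlap check. Replace or supplement the score-distribution check with a table for the kernel-weighted sample containing:
- standardised mean differences for every matching covariate and each Redthread eligibility reason;
- a variance ratio for age, since a mean difference alone can miss unequal spread;
- a short prespecified list of higher-order terms, for example age squared and age by weapon injury.

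Treat an absolute standardised difference above 0.1 as a prompt to review the score model, blind to outcome, and adjust the outcome comparison for covariates that remain imbalanced. Do not require refitting until every entry is below 0.1. With selection fully captured, age squared or weapon by severity still exceeded 0.1 in 27% of runs at 392 per group and 61% at 150. With single-year age bands and three age interactions included, some entry exceeded it in 65 to 88% and 98 to 99% of runs respectively. A compulsory rule would chase noise, especially at pilot size.

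The cost is one extra table and possibly one refit of the score model. The Data collection information table already lists demographic and referral data for both groups, with injury severity and risk level for controls, and the score needs the same variables in the treated group, so no new collection is required.

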As a result, we anticipate needing to recruit treatment and control samples from all 13 sites should the project run to a full trial. This will provide us with the maximal opportunity to meet the statistical power needed to assess our primary outcome (re admission). Additionally, where possible and statistical power is met, we will apply the principles of the Cochrane Progress Plus initiative²² to ensure the findings are reported in a manner applicable to the diverse population in these regions. Hence, during the first year pilot, we will not be able to make causal inferences as to the differences between the groups. However, one of the purposes of the first year is to ensure that data collection approaches are feasible.

Impact data analysis

We anticipate that gathering and analysing SDQ and SRDS measures, and NHS held data (regarding patient outcomes) would require NHS REC and HRA approval.

We will analyse the collected data in the following way. First, we will conduct a pre-treatment analysis, looking at summaries and descriptive statistics of the collected data. Our aim here will be to discover any systematic differences between the treatment and the control group. Second, we will apply propensity score matching to remove the systematic differences which may arise between these groups, due to biases related to the aforementioned observed characteristics. This method will create 'matching pairs' of 'similar' individuals. In each pair, one individual will have received the treatment, and one not. The average difference over all such pairs will constitute a reasonable estimate of the average treatment effect. We will test if this effect is statistically significant using statistical hypothesis testing (t-tests). Furthermore, we will examine if the detected differences are clinically significant, besides being statistically significant.

The pre-determined sample size (see earlier discussion of sampling considerations) needed to get what would be the agreed minimum effect should ensure that the study is sufficiently powered.

Appropriate guidelines will be followed for reporting an observational real world evidence trial:

<https://www.equator-network.org/reporting-guidelines/consort-spi/>

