We will aim, as far as possible, to do sub-group analyses. This will depend on, for example, referral source, initial level of risk etc. and it is not possible to know at this stage if the sample size of sub-groups will be sufficient. If not, the results will be indicative, but underpowered. The subgroups of interest will be based on the variables of gender, age and ethnicity.

Some key data issues need to be kept in mind such as incomplete or missing data or the possibility on noncompliance or higher attrition rates than expected. A certain amount of missing data can be handled using a range of possible techniques but we hope that quarterly audits will prevent this from becoming a serious problem.

PSM does not control for the presence of unobserved covariates that can be correlated with both the treatment and the outcome variables. The presence of such unobserved factors could bias our estimates of the average treatment effects. To account for the selection on unobservables, we will use the Rosenbaum (2002)²³ bounds approach. To find out how strongly hidden biases may influence our results, we will thus do a sensitivity analysis following the boundness approach.

Ensuring cultural competence

We will ensure, that the intervention is delivered in a culturally competent way and not excluding people for cultural and linguistic reasons. For example, a common misconception is to consider the BAME population as homogeneous but there are significant cultural and other differences within the BAME populations and we will consider what these differences are and assessing if the mix in the pilot (and efficacy if we progress) provides the diverse mix that is expected for the target population. This will include an understanding of the differences across BAME groups and the diversity in the type of barriers they face. Thus, we will recognise that YP from BAME groups may not be a unified entity and it will be important in the design to incorporate the diversity of opinions and consider if the way the intervention is delivered needs to be tailored to that. That ensures the research design is truly inclusive by accounting for the potential diverse voices (see above section to reference of PROGRESS PLUS framework).²²

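### The protocol specifies kernel matching but analyses one-to-one pairs with t-tests and Rosenbaum bounds; kernel matching forms no such pairs, and a t-test on the matched differences would be anticonservative

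*Protocol*

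**What the plan says.** The subsection on control group data collection, under Impact evaluation activities, explains that "a matched pair comprises two individuals with the same probability of being assigned to the treatment group". It then fixes a different technique, on the ground that the two groups may differ in size: "we will use kernel-based matching". The kernel is named too: "We prefer the Epanechnikov kernel with a bandwidth of 0.06".

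The Impact data analysis section returns to pairs: "This method will create 'matching pairs' of 'similar' individuals", each holding one treated and one untreated person. The estimator follows: "The average difference over all such pairs will constitute a reasonable estimate of the average treatment effect". So does the test: "We will test if this effect is statistically significant using statistical hypothesis testing (t-tests"). The sentence does not say whether the test is paired, one-sample or two-sample, or which variance it uses.

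The same section addresses hidden bias: "To account for the selection on unobservables, we will use the Rosenbaum" bounds approach. It does not say which version of the bounds is meant, or on which matched set they are computed.

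**The concern.** Kernel matching and pair matching produce different data. Under the kernel, each treated person is set against a smoothed average of all controls whose scores lie within the bandwidth, and the same controls serve many treated people. No one-to-one pairs exist over which to average or test.

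Two things are at stake. First, a t-test over the treated-minus-kernel-mean differences treats the control averages as independent and almost free of noise, although they are built from the same controls. Most of the control group's sampling variance drops out, so p-values and intervals look more precise than they are. Second, Rosenbaum bounds limit how far the odds of treatment can differ within a matched pair or a disjoint matched set. Overlapping kernel weights provide neither, so the only named check on hidden bias does not apply directly to the kernel estimate.

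**Working it through.** **Inputs from the protocol.** Epanechnikov kernel, bandwidth 0.06; 392 per group, with similar group sizes intended (Sample size); an illustrative control risk of 7.8% (Sample size). Two-sided alpha of 0.05 is assumed, since none is stated.

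**The plan's own figure.** n = 2 × (1.96 + 0.842)² / 0.2² ≈ 392.5 per group, or 393 rounded up; 392 gives power of 0.7996. The stated 392 therefore reproduces. This formula charges sampling variance for both groups.

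**Closed form.** Let w_j be the average weight of control j over all treated people, so the weights sum to 1.

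- Variance of the kernel estimate ≈ σ²(1/n₁ + Σw_j²) = σ²(1/n₁ + 1/n₀,eff), where n₀,eff = 1/Σw_j².
- Variance used by a one-sample t-test on the differences ≈ σ²/n₁, because the kernel means vary little from one treated person to the next.
- Ratio of the t-test SE to the true SE = √[(1/n₁) / (1/n₁ + 1/n₀,eff)].

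With every control fully used:

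- 392:392: √(1/2) = 0.707, so 29% too small. Type I error = P(|Z| > 1.96 × 0.707 = 1.386) ≈ 17%.
- 392:1,176: √(1/(1 + 1/3)) = 0.866, so 13% too small. Type I error = P(|Z| > 1.697) ≈ 9%.

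Imbalance concentrates the weights and lowers n₀,eff. At 392:392 with 0.5 SD separation, n₀,eff is about 303, giving √(303/695) = 0.66.

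**Simulation.** Assumptions not taken from the protocol: four normal covariates, an estimated logistic score, groups separated by 0 to 1.0 SD, covariates also related to risk, no treatment effect, 500 replicates. Rejection is measured around the mean estimate, so it isolates the variance error from residual bias. Cells show mean SE / true SD, then type I error.

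| Groups | Separation (SD) | t on pair-type differences | Unweighted two-sample t | Two-sample with kernel weights |
|---|---|---|---|---|
| 392:392 | 0 | 0.715; 16.6% | 1.017; 4.2% | 1.024; 4.0% |
| 392:392 | 0.3 | 0.668; 21.0% | 0.922; 6.8% | 0.963; 5.4% |
| 392:392 | 0.5 | 0.659; 21.4% | 0.890; 9.0% | 0.988; 6.2% |
| 392:392 | 0.8 | 0.561; 26.6% | 0.734; 15.4% | 0.928; 6.2% |
| 392:392 | 1.0 | 0.468; 37.4% | 0.600; 23.8% | 0.860; 9.2% |
| 392:784 | 0 | 0.848; 10.0% | 1.041; 3.4% | 1.045; 3.4% |
| 392:784 | 1.0 | 0.624; 21.4% | 0.717; 15.0% | 0.939; 7.8% |
| 392:1,568 | 0 | 0.861; 9.2% | 0.963; 5.0% | 0.964; 5.0% |
| 392:1,568 | 1.0 | 0.723; 16.6% | 0.777; 14.0% | 0.928; 6.6% |

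Monte Carlo error on a rate of 21% is √(0.21 × 0.79 / 500) ≈ 1.8 percentage points. The ratios carry about 3% relative error (1/√1000).

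**Other simulations.** A separate simulation with two covariates gave, at 392:392, a t-test SE of 0.0148 against a true SD of 0.0229 (ratio 0.65) and type I error of 21%. At 392:1,176 it gave a true SD of 1.19 times the t-test SE (16% too small) and type I error of 10%. Over a range of imbalance at 392:1,176, the SE was 13 to 23% too small and type I error 8 to 14%.

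**The case against.** The strongest reply is that the protocol never says the t-test is paired. A two-sample comparison carrying the kernel weights would be close to valid, and the choice of variance is often left to a statistical analysis plan, which is not at hand. This stands in part. A reader might infer that the stated test gives standard errors one-third too small as a fixed property. The text does not support that: the size depends on the t-test version, the ratio of controls to treated, and the overlap of the scores. The protocol expects historic data to offer more cases to draw on, and a larger control pool shrinks the error. The contradiction itself remains, because the protocol names both the kernel and the pairs. A plain two-sample t-test is no safe escape either, since it is also anticonservative once the groups are imbalanced.

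A second reply is that the Sample size section disclaims causal inference in the pilot, and the efficacy study will have its own protocol. So one cannot say that a confirmatory p-value in this pilot is invalid. But the Outputs section promises a statistical comparison of treated and control groups, and the Success criteria section says the pilot data may enter the final analyses. The specification is therefore likely to be carried forward.

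A reader might also object that the bounds are said to account for hidden bias when they only gauge it. The next sentence calls them a sensitivity analysis, so this is loose wording. Likewise, writing average treatment effect where matching controls to the treated would give the effect in the treated is a labelling matter. No numerical consequence was shown for it.

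**Conclusion.** The protocol contradicts itself: the kernel method it fixes cannot supply the pairs that its estimator and test describe, or those that pair-based bounds need. This holds whatever the data look like.

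The inferential cost is conditional. It applies if the t-test is run on treated-minus-kernel-mean differences, as averaging over pairs suggests, and it assumes 7.8% risk, no true effect, two-sided 5% testing and the simulated covariate structures. At 392:392 with up to 0.5 SD of imbalance, the SE is about 28 to 34% too small and type I error about 16 to 21%. At 1.0 SD these reach 53% and 37%. At 392:1,176 they are about 13 to 23% and 8 to 14%. A variance using the kernel weights gives about 4 to 6% at 392:392 up to 0.5 SD and drifts to 9% only at the strongest imbalance.

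This should be fixed before the specification passes to the efficacy study. It does not undermine the pilot's feasibility aims.

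**What to change.** Make the matching and the inference agree, in one of two ways.

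**(a) Keep the kernel estimator.** Remove the description of pairs. State that the estimate is a risk difference in the treated, with a 95% confidence interval. Take the interval from a variance that carries the kernel weights, or from a bootstrap that re-estimates the propensity score and re-matches in every resample. If Rosenbaum bounds are kept, say that they are computed on a secondary 1:1 matched set and gauge that estimate, not the kernel one. Otherwise, name a sensitivity analysis suited to weighted estimates.

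**(b) Change to 1:1 caliper matching.** Use a paired binary analysis and pair-based (McNemar or Mantel-Haenszel) Rosenbaum bounds. The existing wording about pairs then fits, and the bounds apply to the main estimate. Surplus controls go unused, which matters because the kernel was chosen for unequal group sizes.

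Either way the change is a few sentences and a little standard code, with no new data. Intervals will be wider than those from the pair-difference t-test.

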For power calculations, acceptable levels of differences of outcome in the treatment group compared to the control group for the intervention to be considered a success would be established. Our considerations of sample size and minimally acceptable levels would also be informed by the existing literature in this area. A measure for this effect size is Cohen's d ,²¹ which takes positive values. Cohen suggested that $d = 0.2$ represents a 'small' effect size, 0.5 represents a 'medium' effect size and 0.8 a 'large' effect size. In the current study, we will aim to detect even 'small' effect sizes, i.e. where d takes values around 0.2 . Such effect sizes may be small, but they are meaningful in the current context and are standard in medical research, where sizes in the 0.05 to 0.2 range are frequently encountered. For $d=0.2$, with power of 80% , and assuming treatment and control groups of similar size, the minimum necessary sample is 392 individuals in each group, to a total of 784 . We will aim to use treatment and control samples of similar size. This is likely to be more feasible if constructing the control group from historic data, as there will be more suitable cases to draw on. If treatment and control groups are of unequal size, power calculations can be modified. Thus, the roughly 900 people who are engaged in a longer term programme over the 3 year course will give us adequate power provided the attrition rate is not much more than 50% . This is in line with previous studies conducted.

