On its own, the Cohen's d measure of effect size can be used to understand the relative differences between the treatment and the control group. Absolute differences need information on the averages of the outcome variables of interest in the control group. We can illustrate using some figures regarding the average readmissions in the control group from past literature. These figures are based on Cheng et al. (2008), one of the first emergency department studies.¹⁰ Cheng et al. (2008)¹⁰ analysed pupils $10-15$ years old with peer assault injury in two large hospital emergency departments in Baltimore US. They find that 7.8% of the pupils in the control group had a repeat injury associated with serious youth violence or exploitation. Assuming that we will see the same resubmissions in a control group (which has 392 individuals), this means that we are expecting that 31 (7.8%) of them will be readmitted to the hospital with repeat injuries. It is straightforward to see that the hospital readmissions variable follows a binomial distribution with mean 31 and variance 28.19 . Based on this, unreported calculations show that an intervention with a Cohen's d effect size of 0.2 will have 30 treatment group injury readmissions. If the effect of the intervention is stronger, say $d=0.5$, then the treatment group readmissions are expected to be 28 .

The above analysis depends crucially on the recidivism rate of the control group, which is estimated to be 7.8% in the study of Cheng et al. (2008).¹⁰ In the UK, this rate can be very different because of the different socio-economic conditions. The UK literature currently provides no empirical evidence on outcomes gathered in the UK context.³ As explained above, these estimates are based on a US study and meant to be illustrative. We will gather historical data on the outcomes of interest e.g. readmission to understand what an effect size translates into in terms of a percentage reductions (or increases) from baseline means. This will allow us to benchmark this in terms of the effect seen in similar programmes.

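### The sample-size section turns Cohen's d into readmission counts with the SD of the group total, so the counts shown for d = 0.2 and d = 0.5 are about 20 times too small on the scale that gives 392 per group

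*Protocol*

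**What the plan says.** Under Methods, Sample size, the protocol sets its target: "we will aim to detect even 'small' effect sizes, i.e. where d takes values around 0.2". It states that for d = 0.2, "with power of 80"% and groups of similar size, "the minimum necessary sample is 392 individuals in each group". It expects roughly 900 treated young people over three years and regards power as adequate if attrition is not much above 50%.

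The same section then illustrates d in absolute terms. It takes a 7.8% control risk from a US emergency-department trial, which is 31 of 392, and states that "the hospital readmissions variable follows a binomial distribution with mean 31 and variance 28.19". From calculations it does not report, it concludes that an intervention with a d "effect size of 0.2 will have 30 treatment group injury readmissions". For d = 0.5 it says "then the treatment group readmissions are expected to be" 28.

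The Outcomes section says of the primary outcome that "we are confident that there will be sufficient power to distinguish the two groups". Impact data analysis plans the test: "We will test if this effect is statistically significant using statistical hypothesis testing (t-tests"). No significance level is given.

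**The concern.** The section uses d on two scales. The formula behind 392 per group divides the difference in means by the SD of one person's outcome. The illustration multiplies d by the SD of a count summed over 392 people. The two scales differ by a factor of sqrt(392), about 20.

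The 30 and 28 are the protocol's only absolute translation of its target effect on the primary outcome. A reader who sets them beside the 80% power would take the study to be sized for a difference of about one readmission in 392. The sample is in fact sized for about 18 fewer. A reduction of a quarter or a half could then be missed more often than readers expect, and a null result could be read as evidence of no useful effect. The section also plans to use historical data to express effect sizes as percentage changes, so the faulty conversion could be carried into that step.

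**Working it through.** **Inputs (Protocol, Sample size):** d = 0.2; power 80%; equal groups; 392 per group; control risk p = 0.078; variance 28.19; stated treated counts 30 and 28. **Assumed, because not stated:** two-sided 5%.

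**1. Reproduce 392.** n = 2 × (1.96 + 0.84)² / 0.2² = 392. More exact quantiles or a t-test give 393. One-sided 5% gives 310, so two-sided 5% is the level that fits. Here d is scaled by the per-person SD.

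**2. Reproduce 30 and 28.**
- 392 × 0.078 = 30.58, rounded to 31.
- 392 × 0.078 × 0.922 = 28.19, which is the variance of the group total.
- SD of the total = sqrt(28.19) = 5.31.
- 31 − 0.2 × 5.31 = 29.94, the stated 30.
- 31 − 0.5 × 5.31 = 28.35, the stated 28.

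**3. What the stated counts mean per person.** Per-person SD = sqrt(0.078 × 0.922) = 0.268.
- 31 vs 30: (1/392) / 0.268 = 0.0095, about 0.01.
- 31 vs 28: (3/392) / 0.268 = 0.029, about 0.03.

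**4. What d = 0.2 means from 7.8%.**

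| Scaling | Treated risk | Treated readmissions of 392 | Relative reduction |
|---|---|---|---|
| Pooled SD | 3.25% | 12.8 | 58% |
| Arcsine difference (Cohen's h) | 3.3% | 13.0 | 58% |
| Control SD only | 2.4% | 9.6 | 69% |

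**5. Power at 392 per group** (two-sided 5%, unmatched two-proportion z-test).

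| Comparison | Power |
|---|---|
| 31 vs 30 | 5.2% |
| 31 vs 28 | 6.9% |
| 7.8% reduced by a quarter | about 19% |
| 7.8% halved | about 64% |
| 7.8% to about 3.2% (31 vs 13) | 80% |

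One-sided 5% gives 6.5% for 31 vs 30. Reaching 80% power for 31 vs 30 would need about 173,000 per group.

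**6. Sensitivity to group size and control risk** (same test, 80% power).

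| Per group | Control risk | Detectable relative reduction |
|---|---|---|
| 392 | 3.9% | 78% |
| 392 | 7.8% | 58% |
| 392 | 15.6% | 42% |
| 900 | 7.8% | 41% (to about 4.6%) |

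At 7.8%, power for a halving is about 70% with 450 per group and 94% with 900.

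**The case against.** **The 392 is correct for d = 0.2.** This stands. A reader might infer that the claimed 80% power does not exist at all, but the documents do not support that. The power claim is attached to d, and for a per-person d of 0.2 it is right. The protocol also never states a power for 31 vs 30; that link is the reader's inference from adjacent paragraphs.

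**The figures are called illustrative.** That caveat is about the US control risk. The conversion is wrong at any control risk.

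**392 is a minimum.** This stands in part. With 900 per group and no attrition the detectable fall is about 41%, so 58% should not be presented as the study's only capability. Neither figure comes near one readmission in 392.

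**This is a pilot, and funding does not turn on the counts.** This stands as to consequence. A reader might infer that the decision to proceed to the efficacy study rests on the wrong figure. The progression criteria concern delivery, recruitment, eligibility, retention and data matching, and none uses a detectable effect. The pilot disclaims causal inference and the efficacy study would have its own protocol. The calculation is nonetheless offered as the justification for the three-year sample.

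**d = 0.5 is out of reach, so that sentence is impossible.** This is tempting but depends on the metric. With no treated readmissions at all, d is 0.29 on the control SD and 0.41 on the pooled SD, but the arcsine measure reaches about 0.57.

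**The confidence about power is a general statement.** True. It does not cite the counts, so it needs qualifying rather than correcting as arithmetic.

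**Conclusion.** The point holds as an error of conversion. Both stated counts are reproduced by using the SD of the group total, whereas 392 per group rests on the per-person SD. At a 7.8% control risk, d = 0.2 corresponds to about 31 vs 13 readmissions (10 on the control SD), not 31 vs 30. The pairs shown for d = 0.2 and d = 0.5 are per-person effects of about 0.01 and 0.03, with power of about 5% and 7%.

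The sample size need not change for the stated d. What changes is its meaning: at this control risk an effect labelled small removes more than half of readmissions. The power figures assume two-sided 5%, equal groups and an unmatched two-proportion test. The protocol plans kernel matching and t-tests, so they are a guide to the planned analysis and not an exact account of it.

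**What to change.** In Sample size, delete the two sentences giving 30 and 28 treated readmissions. Replace them with the following, labelling the assumptions (two-sided 5%, unmatched two-proportion test, equal groups):

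> With 392 per group and a 12-month control risk of 7.8%, the study has 80% power to detect a fall to about 3.2% (about 31 vs 13 readmissions, a 58% relative reduction). Power is about 64% for a halving and about 19% for a 25% reduction. With 900 per group and no attrition, the detectable fall is to about 4.6% (41%).

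Add the same line for other control risks: at 392 per group, a 78% relative reduction at 3.9% and 42% at 15.6%. Use the per-person SD when historical data later replace the US figure.

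Keep the d = 0.2 target, but say that at a 7.8% control risk it means removing more than half of readmissions. Qualify the small-effect wording, and the confidence about sufficient power in Outcomes and in Mechanism for action and key outcomes, to match.

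The cost is protocol wording only. The stated detectable effect becomes less favourable.
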